3.2 Exclusion Criteria

- The patient has either clinically apparent central nervous system metastases or carcinomatous meningitis
- The patient is a woman who is pregnant or lactating. Women of childbearing potential must have a negative serum pregnancy test performed within 7 days prior to the start of study drug. Post-menopausal women (defined as no menses for at least 1 year) and surgically sterilized women are not required to undergo a pregnancy test. All patients (men and women) of childbearing potential must agree to use adequate contraception beginning at the signing of the ICF until at least 30 days after the last dose of study drug. The definition of adequate contraception will be based on the judgment of the principal investigator or a designated associate.
- Active or clinically significant cardiac disease including:
 - Congestive heart failure New York Heart Association (NYHA) > Class II.
 - Active coronary artery disease.
 - Cardiac arrhythmias requiring anti-arrhythmic therapy other than beta blockers or digoxin.
 - QTc > 500 ms
 - Unstable angina (anginal symptoms at rest), new-onset angina within 3 months before randomization, or myocardial infarction within 6 months before randomization.
- Evidence or history of bleeding diathesis or coagulopathy.
- Subject with any pulmonary hemorrhage/bleeding event of NCI-CTCAE v4.0 Grade 2 or higher within 4 weeks before enrollment; any other hemorrhage/bleeding event of NCI-CTCAE v4.0 Grade 3 or higher within 4 weeks before enrollment.
- Presence of a non-healing wound, non-healing ulcer, or bone fracture.
- History of organ allograft. (including corneal transplant).
- Any malabsorption condition.

- Uncontrolled hypertension defined as systolic blood pressure > 150 mmHg or diastolic pressure > 90 mmHg, despite optimal medical management.
- Uncontrolled ascites defined as not easily controlled by stable doses of diuretics.
- Known human immunodeficiency virus (HIV) infection.
- The patient has a medical or psychiatric condition that constitutes an unacceptable risk for participation in this trial, in the judgment of the treating physician.
- The patient has received any investigational agents within 4 weeks prior to their first dose of sorafenib.
- ECOG status of ≥ 2
- Child-Pugh B or C cirrhosis (CTP score \geq 7) (See Appendix A)
- CLIP score >3 (See Appendix A) Inability to comply with study and/or follow-up procedures

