10.0 Evaluation of Response

All patients with measurable disease who have received the first cycle of treatment and had a tumor re-assessment will be considered evaluable for response. In addition, those patients who develop early progressive disease or who discontinue early from the study due to toxicity will also be considered evaluable for response. Patients on therapy for at least the first cycle of treatment will have their responses classified according to the definitions below.

Response and progression will be evaluated in this study using the international criteria proposed by the RECIST (Response Evaluation Criteria in Solid Tumors (RECIST 1.1) committee. Changes in only the largest diameter (unidimensional measurement) of the tumor lesions are used in the RECIST criteria.

10.1Definitions

Measurable disease - the presence of at least one measurable lesion. If the measurable disease is restricted to a solitary lesion, its neoplastic nature should be confirmed by cytology/histology.

Measurable lesions - lesions that can be accurately measured in at least one dimension with longest diameter \ge 20 mm using conventional techniques or \ge 10 mm with spiral CT scan.

Non-measurable lesions - all other lesions, including small lesions (longest diameter <20 mm with conventional techniques or <10 mm with spiral CT scan), i.e., bone lesions, leptomeningeal disease, ascites, pleural/pericardial effusion, inflammatory breast disease, lymphangitis cutis/pulmonis, cystic lesions, and also abdominal masses that are not confirmed and followed by imaging techniques, cystic lesions and lesions occurring within a previously irradiated area unless they are documented as new lesions since the completion of radiation therapy.

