Target/Non-target Lesions - all measurable lesions up to a maximum of five lesions per organ and 10 lesions in total, representative of all involved organs should be identified as *target lesions* and recorded and measured at baseline. Target lesions should be selected on the basis of their size (lesions with the longest diameter) and their suitability for accurate repeated measurements (either by imaging techniques or clinically). A sum of the longest diameter (LD) for *all target lesions* will be calculated and reported as the baseline sum LD. The baseline sum LD will be used as reference by which to characterize the objective tumor. All other lesions (or sites of disease) should be identified as *non-target lesions* and should also be recorded at baseline. Measurements of these lesions are not required, but the presence or absence of each should be noted throughout follow-up.

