10.2 Response Criteria

Method of Tumor Response Assessment

The same method of assessment and the same technique should be used to characterize each identified and reported lesion at baseline and at reassessment during treatment. Imaging-based evaluation is preferred to clinical examination. Clinical lesions will only be considered measurable when they are superficial (e.g., skin nodules and palpable lymph nodes). For the case of skin lesions, documentation by color photography, including a ruler to estimate the size of the lesion, is recommended. CT and MRI are the best currently available and reproducible methods to measure target lesions selected for response assessment. Conventional CT and MRI should be performed with cuts of 10 mm or less in slice thickness contiguously. Spiral CT should be performed using a 5 mm contiguous reconstruction algorithm. Lesions on chest X-ray are acceptable as measurable lesions when they are clearly defined and surrounded by aerated lung. However, CT is preferable. Ultrasound is not an acceptable method of disease assessment.

Definition of Response

Overall tumor response will be based on an integration of the evaluation of target, non-target, and new lesions, as described below:

Evaluation of target lesions

Complete Response (CR): Disappearance of all clinical and radiological evidence of target lesions.

Partial Response (PR): A 30% or greater decreased in the sum of LD of all lesions in reference to the baseline sum LD.

Stable Disease (SD): Neither sufficient increase to qualify for PD nor sufficient shrinkage to qualify for PR.

Progressive Disease (PD): A 20% or greater increase in the sum of LD of all target lesions, taking as reference the smallest sum LD recorded since baseline.

To be assigned a status of PR or CR, changes in tumor measurements must be confirmed by repeat evaluations which should be performed no less than 4 weeks after the criteria for response are first met.

Evaluation of non-target lesions

Complete Response (CR): Disappearance of all non-target lesions.

Non-Complete Response, Non-Progressive Disease (Non-CR, Non-PD): Persistence of one or more non-target lesions.

Progressive Disease (PD): Unequivocal progression of existing non-target lesion(s).

Note: Increased uptake on bone scan alone is insufficient evidence of progression; additional evidence of progressive disease would be present to declare unequivocal progression.

Evaluation of new lesions

No: There are no new lesions.

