S-FOLFOX in HCC

Yes: New lesions are present. Note: If new lesions are present, the patient is considered to have progressive disease overall.

Overall Response

Overall response will be determined as tabulated below, based on the evaluation of target, non-target, and new lesions:

Target lesions	Non-Target lesions	New Lesions	Overall response
CR	CR	No	CR
CR	Incomplete response/SD	No	PR
PR	Non-PD	No	PR
SD	Non-PD	No	SD
PD	Any	Yes or No	PD
Any	PD	Yes or No	PD
Any	Any	Yes	PD

To be assigned a status of PR or CR, changes in tumor measurements must be confirmed by repeat assessments that should be performed no less than 4 weeks after the criteria for response are first met. Longer intervals as determined by the study protocol may also be appropriate.

In the case of SD, follow-up measurements must have met the SD criteria at least once after study entry at a minimum interval (in general, not less than 6-8 weeks) that is defined in the study protocol.

Every effort should be made to document tumor measurements and extent of disease, even after discontinuation of therapy, in order to classify patients for overall response as described above. Patients who do not have tumor response assessment due to rapid progression or toxicity will be considered as non-responders, will be included in the denominator for the response rate, and will be classified into one of the following categories:

- death attributed to disease progression
- deterioration attributed to disease progression
- death attributed to drug toxicity
- early discontinuation attributed to drug toxicity

Note: If a patient receives subsequent therapy before tumor progression is documented, the reason for changing therapy must be reported; reasons

include clinical progression, drug toxicity, or secondary therapy for maintenance of tumor response.

Duration of Overall Response

The duration of overall response is measured from the time measurement criteria are met for CR or PR (whichever status is recorded first) until the first date that recurrence or PD is objectively documented, taking as reference for PD the smallest measurements recorded since the treatment started. Patients who do not relapse will be censored at the day of their last tumor assessment.

Time to response

Time from date of initial treatment until first objective documentation of response.

Time to tumor progression

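### Ascites and effusions are listed as non-measurable lesions with no requirement that they be malignant, so benign fluid in a Child-Pugh A patient can be scored as progression and end TTP

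*Combined protocol and SAP*

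**What the plan says.** The rule is built up in steps across section 10 of the combined protocol and SAP.

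- **10.1, non-measurable lesions.** The list begins "i.e., bone lesions, leptomeningeal disease, ascites, pleural/pericardial effusion". No condition on malignancy is attached. The same list names inflammatory breast disease, which suggests generic text not adapted to HCC.
- **10.1, target and non-target lesions.** "All other lesions (or sites of disease) should be identified as" non-target lesions, to be recorded at baseline and followed.
- **10.2, non-target lesions.** PD is "Unequivocal progression of existing non-target lesion(s").
- **10.2, new lesions.** "If new lesions are present, the patient is considered to have progressive disease overall". This rule carries no qualifier such as unequivocal.
- **10.2, time to tumor progression.** The clock stops at the first documented PD or at death. Section 14.2.1 makes TTP the primary endpoint.

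Two guards appear in section 10, and neither covers fluid. One is for measurable disease: "If the measurable disease is restricted to a solitary lesion, its neoplastic nature should be confirmed by cytology/histology". The other is for bone scans: "Increased uptake on bone scan alone is insufficient evidence of progression".

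On entry, 3.1 admits patients without cirrhosis or with Child-Pugh A cirrhosis (CTP below 7). Section 3.2 excludes only "Uncontrolled ascites defined as not easily controlled by stable doses of diuretics". In Appendix A slight ascites scores 2 points, and Grade A runs from 5 to 6.

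**The concern.** In cirrhosis, ascites and effusions can come from the liver disease rather than the tumour. The protocol admits patients who may already have controlled ascites, and its own definitions then allow that fluid to be recorded as a tumour lesion. Another patient may develop fluid on treatment for reasons unrelated to tumour growth.

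A reader who follows the text could therefore call PD with all measured tumours stable or shrinking. The primary endpoint would then mix liver decompensation with tumour progression. Progression-free survival in 14.2.2 rests on the same progression call. Because 5.1.6 and 6.5 list disease progression among the reasons treatment ends, a misread scan would affect more than the endpoint date.

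**Working it through.** **1. Can an eligible patient have benign ascites at baseline?** From Appendix A, slight ascites scores 2 and the other four items score 1 at best: 2 + 1 + 1 + 1 + 1 = 6. That is Grade A, meets 3.1, and is not excluded by 3.2 if diuretics control the fluid. So yes, although only when every other item is at its best score.

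**2. Does the written rule reach PD?** There are two routes.

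| Situation | Rule | Protection in the text |
|---|---|---|
| Fluid at baseline, later worse | Non-target PD (10.2) | The increase must be unequivocal, but that describes the change and not the cause |
| No fluid at baseline, later present | New lesion, PD overall (10.2) | None stated |

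**3. Reproduce the planned power.** Inputs from 14.2.1: N = 40, null median 5 months, alternative 7 months, one-sided 10%, 18 months of accrual plus 24 months of follow-up. Assume exponential times and a test on the log median with d events:

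power = Φ(√d × ln(m/5) − 1.2816), where m is the median under the alternative.

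- All 40 patients with events: √40 × ln(1.4) = 6.325 × 0.3365 = 2.128. Then Φ(0.846) = 80.1%.
- Expected events, with uniform accrual: P(event) = 0.957 and d = 38.3, giving 78.8%.

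The stated 80% is reproduced and is not in dispute.

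**4. Sensitivity to benign fluid scored as PD.** The documents give no rate, so a share s of TTP events is assumed. With constant hazards and a true median of 7 months, the total hazard is (ln 2/7)/(1 − s), and the observed median is 7 × (1 − s).

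| Assumed s | Observed median (months) | Expected events d | Fluid events, s × d | Power at d | Power at 40 events |
|---|---|---|---|---|---|
| 0 | 7.00 | 38.3 | 0 | 78.8% | 80.1% |
| 5% | 6.65 | 38.5 | 1.9 | 68.7% | 69.9% |
| 10% | 6.30 | 38.8 | 3.9 | 56.2% | 57.1% |

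As a worked line for s = 10%: √38.8 × ln(6.30/5) = 6.229 × 0.2311 = 1.440. Then Φ(1.440 − 1.2816) = Φ(0.158), about 56%.

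**5. Direction.** If the true median were 5 months, the same shares would lower the chance of rejecting the null from 10% to 5.4% (s = 5%) and 2.6% (s = 10%). The distortion does not produce false positives against a fixed 5-month null.

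**The case against.** The strongest reply is that the list need not be read literally. Section 10.0 speaks of tumour lesions and 10.1 of sites of disease, so the list may name forms of tumour that cannot be measured rather than declare all fluid to be tumour. Section 10.0 also states "Response and progression will be evaluated in this study using the international criteria proposed by the RECIST" committee (version 1.1). The text of those criteria is not part of the documents, so whether they supply a rule on fluid cannot be checked here. This reading is possible, but the protocol's own wording does not settle it. It took care to guard against over-reading bone scans and did not do the same for fluid.

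Several stronger inferences are tempting, and the documents do not support them:

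- **That toxicity is moved out of the safety data.** Section 11.1 defines an adverse event regardless of cause, and 14.2.2 records all toxicity. An event scored as PD is still reportable; at most it counts in both places.
- **That persistent ascites lowers the response rate.** The table in 10.2 scores a target CR with incomplete non-target response as PR, and 14.2.2 counts CR and PR together. The label can change from CR to PR, but the rate does not.
- **That any increase in existing fluid is PD.** It must be unequivocal.
- **That the trial sample is known to be mostly cirrhotic.** Section 2.1 says this of HCC in general. Section 3.1 also admits patients without cirrhosis and gives no expected share.
- **That the power loss is an estimate.** The shares are assumed. The model treats every such fluid event as scored PD and as independent of death and true progression. Death already ends TTP, and decompensation plausibly clusters near death or progression, so the added effect could be smaller.

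The benchmark matters too. The 5- and 7-month medians sit near TTPs quoted from earlier trials (5.5 months in 2.2 and 2.3, 7.1 months in 2.4). If fluid was scored the same way in the data behind the null, much of the distortion would already be in the comparison.

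**Conclusion.** The point holds as a gap in the endpoint definition. As written, section 10 permits benign ascites or an effusion to be scored as progression in the primary endpoint, and the entry criteria admit patients in whom this can happen. New fluid is the more exposed route, because the new-lesion rule has no qualifier.

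The likely effect is a shorter observed TTP, which counts against the regimen and risks a false negative, unless the 5-month benchmark carries the same convention. The size cannot be established from the documents. The table above is an upper-end illustration that rests on assumed shares, constant hazards, full misclassification and independence from other events. Its use is to show that with 40 patients and 2 months between the hypotheses, about two to four misclassified events would be enough to matter. The correction is worth making because it is cheap.

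**What to change.** In 10.1 and 10.2, state that ascites or a pleural or pericardial effusion is not by itself a non-target or new lesion, and cannot alone establish PD or prevent CR, unless malignant cells have been shown in fluid sampled for clinical reasons. Record other new or worsening fluid as an adverse event.

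If scans have already been scored, keep the scored result and report TTP with and without fluid-only progressions as a sensitivity analysis. This is likely to apply if the planned schedule held: this version is dated February 2015, against an estimated July 2012 start (5.1.5) and accrual within 18 months (14.1).

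**Cost.** The wording adds no procedure. The sensitivity analysis requires identifying which progressions rested on fluid alone, which may mean going back to the response records or scans. One downside remains: malignant fluid that is never sampled would not be called PD until another tumour finding or death. That may slightly lengthen TTP, which in a single-arm trial favours the regimen, and is a further reason to show both analyses.

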10.2 Response Criteria

Method of Tumor Response Assessment

The same method of assessment and the same technique should be used to characterize each identified and reported lesion at baseline and at reassessment during treatment. Imaging-based evaluation is preferred to clinical examination. Clinical lesions will only be considered measurable when they are superficial (e.g., skin nodules and palpable lymph nodes). For the case of skin lesions, documentation by color photography, including a ruler to estimate the size of the lesion, is recommended. CT and MRI are the best currently available and reproducible methods to measure target lesions selected for response assessment. Conventional CT and MRI should be performed with cuts of 10 mm or less in slice thickness contiguously. Spiral CT should be performed using a 5 mm contiguous reconstruction algorithm. Lesions on chest X-ray are acceptable as measurable lesions when they are clearly defined and surrounded by aerated lung. However, CT is preferable. Ultrasound is not an acceptable method of disease assessment.

Definition of Response

Overall tumor response will be based on an integration of the evaluation of target, non-target, and new lesions, as described below:

Evaluation of target lesions

Complete Response (CR): Disappearance of all clinical and radiological evidence of target lesions.

Partial Response (PR): A 30% or greater decreased in the sum of LD of all lesions in reference to the baseline sum LD.

Stable Disease (SD): Neither sufficient increase to qualify for PD nor sufficient shrinkage to qualify for PR.

Progressive Disease (PD): A 20% or greater increase in the sum of LD of all target lesions, taking as reference the smallest sum LD recorded since baseline.

To be assigned a status of PR or CR, changes in tumor measurements must be confirmed by repeat evaluations which should be performed no less than 4 weeks after the criteria for response are first met.

Evaluation of non-target lesions

Complete Response (CR): Disappearance of all non-target lesions.

Non-Complete Response, Non-Progressive Disease (Non-CR, Non-PD): Persistence of one or more non-target lesions.

Progressive Disease (PD): Unequivocal progression of existing non-target lesion(s).

Note: Increased uptake on bone scan alone is insufficient evidence of progression; additional evidence of progressive disease would be present to declare unequivocal progression.

Evaluation of new lesions

No: There are no new lesions.

S-FOLFOX in HCC

Yes: New lesions are present. Note: If new lesions are present, the patient is considered to have progressive disease overall.

Overall Response

Overall response will be determined as tabulated below, based on the evaluation of target, non-target, and new lesions:

Target lesions	Non-Target lesions	New Lesions	Overall response
CR	CR	No	CR
CR	Incomplete response/SD	No	PR
PR	Non-PD	No	PR
SD	Non-PD	No	SD
PD	Any	Yes or No	PD
Any	PD	Yes or No	PD
Any	Any	Yes	PD

To be assigned a status of PR or CR, changes in tumor measurements must be confirmed by repeat assessments that should be performed no less than 4 weeks after the criteria for response are first met. Longer intervals as determined by the study protocol may also be appropriate.

In the case of SD, follow-up measurements must have met the SD criteria at least once after study entry at a minimum interval (in general, not less than 6-8 weeks) that is defined in the study protocol.

Every effort should be made to document tumor measurements and extent of disease, even after discontinuation of therapy, in order to classify patients for overall response as described above. Patients who do not have tumor response assessment due to rapid progression or toxicity will be considered as non-responders, will be included in the denominator for the response rate, and will be classified into one of the following categories:

- death attributed to disease progression
- deterioration attributed to disease progression
- death attributed to drug toxicity
- early discontinuation attributed to drug toxicity

Note: If a patient receives subsequent therapy before tumor progression is documented, the reason for changing therapy must be reported; reasons

include clinical progression, drug toxicity, or secondary therapy for maintenance of tumor response.

Duration of Overall Response

The duration of overall response is measured from the time measurement criteria are met for CR or PR (whichever status is recorded first) until the first date that recurrence or PD is objectively documented, taking as reference for PD the smallest measurements recorded since the treatment started. Patients who do not relapse will be censored at the day of their last tumor assessment.

Time to response

Time from date of initial treatment until first objective documentation of response.

Time to tumor progression

Time from date of initial treatment to first objective documentation of progressive disease or death. Patients who die without a reported prior progression will be considered to have progressed on the day of their death.

Time to treatment failure

Time from date of initial treatment to first objective documentation of progressive disease, or off study date, whichever occurs first.

Time to death

Time from date of initial treatment to date of death

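### Section 10.2 sets no millimetre minimum for target-lesion progression, so when the smallest target sum is under 25 mm a rise of less than 5 mm can end TTP

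*Combined protocol and SAP*

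**What the plan says.** Section 10.2 (Evaluation of target lesions) calls progression at "A 20% or greater increase in the sum of LD of all target lesions, taking as reference the smallest sum LD recorded since baseline", where LD is the longest diameter. Neither Section 10 nor any other part of the protocol states a minimum rise in millimetres.

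Section 10.1 sets the lower end of that sum. Measurable disease is "the presence of at least one measurable lesion", and a lesion qualifies from "10 mm with spiral CT scan", or from 20 mm with conventional techniques. On image acquisition, Section 10.2 says: "Spiral CT should be performed using a 5 mm contiguous reconstruction algorithm", and "Conventional CT and MRI should be performed with cuts of 10 mm or less in slice thickness contiguously".

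Confirmation is one-sided: "To be assigned a status of PR or CR, changes in tumor measurements must be confirmed by repeat evaluations". No matching sentence exists for PD. The overall-response table carries target PD straight through, whatever the other lesions show: "PD Any Yes or No PD". TTP is then "Time from date of initial treatment to first objective documentation of progressive disease or death".

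Sections 5.2.2 and 10.0 name RECIST 1.1 as the criteria, but do not reproduce it. Section 10.0 also says that patients are classified by the definitions it goes on to write out, and those contain no minimum.

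**The concern.** A purely relative threshold shrinks with the tumour sum. For a small sum it falls to a few millimetres, a size that two readings of an unchanged lesion might differ by. The reference is the smallest sum recorded, so a patient whose lesions shrink moves to a tighter trigger: a 10 mm lesion that falls 30% to 7 mm needs a rise of only 0.20 × 7 = 1.4 mm. The rule applies at each 8-weekly scan, and one reading is enough.

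TTP is the primary endpoint in a single arm of 40 patients, compared with a fixed null median of 5 months (Section 14.2.1). No concurrent control arm shares the same measurement error. Any false PD shortens observed TTP.

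**Working it through.** **1. The plan's own figure.** Section 14.2.1 gives N = 40, null median 5 months, alternative 7 months, one-sided 10% and 80% power. For a one-sample exponential test on the log scale:

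events = ((1.2816 + 0.8416) / ln(7/5))² = (2.1232 / 0.3365)² = 39.8, so 40.

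Power at 40 events is 80.1%. Allowing for censoring with 18 months of accrual and 24 of follow-up, 38.3 events are expected under the alternative, and power is 78.8% (log scale) or 80.7% (mean scale). The stated 80% reproduces. The progression rule does not enter this calculation.

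**2. Size of the trigger.** Minimum rise counted as PD = 0.20 × smallest recorded sum.

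| Smallest sum (mm) | 7 | 10 | 15 | 20 | 25 | 50 |
|---|---|---|---|---|---|---|
| Trigger (mm) | 1.4 | 2 | 3 | 4 | 5 | 10 |

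The trigger reaches 5 mm at a sum of 5 / 0.20 = 25 mm.

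**3. False PD at one comparison.** Assumptions, none of them in the documents: no true growth; two readings X (reference) and Y (current) of a sum s, each with independent normal error of standard deviation σ; σ from 0.5 to 2 mm.

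As written: P(Y ≥ 1.2X) = 1 − Φ(0.2s / (σ√(1 + 1.2²))) = 1 − Φ(0.2s / (1.562σ)).

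Rise of 5 mm or more: P(Y − X ≥ 5) = 1 − Φ(5 / (1.414σ)). At sums up to 20 mm this is, to rounding, the rate with a 5 mm minimum added to the 20% rule.

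Worked case, s = 10 and σ = 1: as written 1 − Φ(2 / 1.562) = 1 − Φ(1.28) = 10.0%; with the minimum 1 − Φ(5 / 1.414) = 1 − Φ(3.54) = 0.02%.

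| s = 10 mm | σ = 0.5 | σ = 1 | σ = 1.5 | σ = 2 |
|---|---|---|---|---|
| As written | 0.5% | 10.0% | 19.7% | 26.1% |
| 20% and 5 mm | 0.0% | 0.02% | 0.9% | 3.9% |

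Simulation with one million pairs agrees within 0.1 percentage point. Treating the trigger as a fixed 2 mm, and so ignoring noise in the reference when setting it, gives 7.9% to 24.0% for σ of 1 to 2 mm.

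**4. Larger sums, at σ = 2 mm.** As written, 10.0% at 20 mm, 5.5% at 25 mm and 0.07% at 50 mm. With the minimum, 3.9%, 3.8% and 0.07%. The small difference left at 25 mm arises because a true 25 mm sum can be read below 25. Once the recorded nadir is 25 mm or more, a 5 mm minimum cannot bind.

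**5. Repeated scans.** Over three follow-up scans judged against the running minimum, simulated cumulative false PD at a 10 mm sum is 37% to 72% as written for σ of 1 to 2 mm, and 0.1% to 17% with the minimum. At σ = 0.5 mm it is 2.7% as written. The minimum reduces the problem but does not remove it if reading error is large.

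**The case against.** Four points on the other side carry weight.

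**The named criteria.** The protocol twice cites RECIST 1.1, and Section 10.2 may be only an abridged restatement. A reader might infer either that the cited criteria supply a minimum or that the plan departs from them. The documents support neither inference, because the text of those criteria is not in them. What stands is that two sources are named for one endpoint, the written one has no minimum, and no sentence says which prevails.

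**Scope.** A reader might infer that a 2 mm change in any 10 mm lesion ends TTP. It does so only if the whole target sum is about 10 mm. Section 10.1 sums all measurable lesions, up to five per organ and 10 in total, chosen for size and for reliable re-measurement. Section 3.1 enrols advanced disease. A solitary target of minimum size is permitted, but nothing shows that it is common.

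**The benchmark.** A reader might infer that 2 mm must be noise because it is less than the 5 mm reconstruction interval. That interval is the spacing between slices. It is not the reading error of a diameter, and the plan does not say in which plane LD is measured. The 5 mm figure is a convenient marker of resolution, and the protocol does not derive a minimum from it.

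**Direction of bias.** A reader might infer that the trial as a whole is biased against benefit. False PD does shorten TTP, but the documents do not say which progression rule lies behind the 5-month null. If that rule had no minimum, adding one only here could lengthen TTP relative to the null.

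**Conclusion.** The gap in the definition is real and its effect is confined to small target sums. As written, a smallest sum under 25 mm can yield a primary event on a rise of less than 5 mm, on one unconfirmed reading. At a 10 mm sum the false-PD rate per comparison is about 0.5% to 26%, against at most about 4% with a 5 mm minimum. Both ranges rest on an assumed reading error of 0.5 to 2 mm with independent normal errors, and at the low end of that range the problem nearly vanishes. The effect on the trial's estimate cannot be sized, because the distribution of target sums is not given. N = 40 and 80% power stand. This is a low-priority improvement that is cheap to make.

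**What to change.** In Section 10.2, for the TTP endpoint, define target-lesion PD as an increase of at least 20% and of at least a stated absolute amount (for example 5 mm) over the smallest recorded sum. Add one sentence to Section 10.0 saying whether the definitions in Section 10 or the named RECIST 1.1 criteria govern where they differ. In Section 14.2.1, pre-specify TTP under the 20%-only rule as a sensitivity analysis, so that comparability with the 5-month null can be judged.

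The cost is one clause, one sentence, a change to the response form and one extra analysis of data already collected. There are two downsides: true small growth in very small lesions may be dated one scan later, and TTP could be slightly longer relative to a null built on a rule without a minimum.

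Disease progression is also listed as a reason to end treatment in Sections 5.1.6 and 6.5. The sponsor should reconcile those sections with the endpoint definition; this point proposes no treatment rule.
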